9.1.1.1 Dose proportionality analysis

Dose-proportionality (an increase in dose corresponds to a proportional increase in PK outcome) after a single dose, will be assessed using the power model, i.e., linear regression modelling of AUC_{0-t} , AUC_{0-inf} , and C_{max} respectively on log-scale according to the formula:

$$\ln(PK) = \beta_0 + \beta_1 \times \ln(dose)$$

Let h be the highest dose and l be the lowest dose. Then the predicted PK geometric mean (back-transformed to normal scale) of the high dose is $e^{\beta_0}h^{\beta_1}$, and that of the low dose is $e^{\beta_0}l^{\beta_1}$. Let r be the maximal dose ratio, i.e., h/l . Dose proportionality corresponds to:

$$e^{\beta_0}h^{\beta_1}/e^{\beta_0}l^{\beta_1} = h/l \rightarrow (h/l)^{\beta_1-1} = r^{\beta_1-1} = 1$$

Let $\Theta_L=0.8$ and $\Theta_H=1.25$ be the lower and upper acceptance limits respectively, (0.8 and 1.25 being the industry standard limits). Dose-proportionality occurs when

$$\Theta_L < r^{\beta_1-1} < \Theta_H,$$

which on natural log scale equates to

$$\ln(\Theta_L) < (\beta_1 - 1)\ln(r) < \ln(\Theta_H) \rightarrow 1 + \frac{\ln(\Theta_L)}{\ln(r)} < \beta_1 < 1 + \frac{\ln(\Theta_H)}{\ln(r)}$$

Specifically, dose-proportionality is declared when the 90% CI for β_1 from the linear regression model on log scale lies entirely within the acceptance region:

$$\left[1 + \frac{\ln(0.8)}{\ln(r)}, 1 + \frac{\ln(1.25)}{\ln(r)}\right]$$

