CONFIDENTIAL

A single-centre, open-label, phase I trial evaluating the pharmacokinetics of single ascending oral doses of IRL757 in healthy elderly volunteers.**PROTOCOL SYNOPSIS**

Version: 2.1
Version date: 02-OCT-2024
Superseded version: Not applicable
Sponsor: Integrative Research Laboratories Sweden AB (IRLAB)
Product: IRL757 [REDACTED]
Trial Number(s): IRL757C002
EU trial no: 2024-515124-36-00
NCT no: NCT06699628

Integrative Research Laboratories Sweden AB (IRLAB)
[name]
[name]
SWEDEN
[contact]

TRIAL SYNOPSIS

Trial Title	
A single-centre, open-label, phase I trial evaluating the pharmacokinetics of single ascending oral doses of IRL757 in healthy elderly volunteers.	
Trial code	EU trial no
IRL757C002	2024-515124-36-00
Trial period	Phase of development
Estimated date of first subject enrolled: Q3 2024	Phase I
Estimated date of last subject completed: Q4 2024	
Trial background	
IRL757 [REDACTED] is a novel small molecule compound developed for the treatment of apathy in neurodegenerative disorders. This is a trial of IRL757 with the aim to study safety, tolerability and PK following single oral doses to healthy elderly volunteers.	
Trial design and trial population	
An open label single oral dose trial in elderly healthy volunteers.	
Objectives	
Primary objective: 
 To determine the single oral dose pharmacokinetic (PK) characteristics of IRL757 and its 3 main metabolites in healthy elderly volunteers. 	
Secondary objectives: 
 To evaluate the safety and tolerability of IRL757 after single oral dosing in healthy elderly volunteers. 	
Exploratory objective: 
 To characterize the metabolite profile in plasma and urine of healthy elderly volunteers. 	
Endpoints	
Primary endpoints: PK assessments 
 AUC_{0-t}, AUC_{0-24h}, $AUC_{0-\infty}$, C_{max}, T_{max}, λ_{z}, $T_{1/2}$, amount excreted in urine (Ae), CL/F, V_z/F, fraction of the dose excreted in urine (Fe) (for IRL757), renal clearance CL_R. Dose proportionality after single doses based on AUC_{0-t}, $AUC_{0-\infty}$ and C_{max}. 	
Secondary endpoints: Safety assessments 
 Frequency, seriousness and intensity of Adverse Events (AEs) Physical examination 	

- Columbia-Suicide Severity Rating Scale (C-SSRS)
- Electrocardiogram (ECG) recordings

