- Vital signs (blood pressure, heart rate and body temperature)
- Safety laboratory measurements

Exploratory endpoints:

- Metabolite profile in plasma
- Profile of excreted metabolites in urine

Number of subjects planned

12 healthy subjects will be included in two dose groups.

Diagnosis and main eligibility criteria

Healthy elderly volunteers ≥ 65 and < 90 years of age, with a weight of 50 to 110 kg, who are willing to comply with trial procedures and who have given written consent, will be considered eligible for participation in the trial.

Methodology

Twelve (12) eligible and consenting subjects will be allocated to two dose groups. All subjects will be assigned to a single dose treatment with IRL757, 6 subjects to dose 1 and 6 subjects to dose 2.

Eligible subjects will be confined to the research clinic from the evening before first dosing (Day -1) until 48 hours following dosing. The subjects should be fasting overnight (10 hours) before dose administration on Day 1. A Follow-up Visit will be performed 5-10 days after administration of IMP.

Investigational Medicinal Products (IMP), dosage and mode of administration

IRL757 half-life is expected to be 4-10 hours.

IRL757 capsules**Duration of treatment**

Subjects included in the study will receive one dose of IRL757.

Duration of each subject's involvement in the trial

Subjects will be screened for eligibility according to trial-specific inclusion/exclusion criteria at Visit 1 (Screening visit) within 28 days prior to IMP administration.

A Follow-up Visit will be performed for all subjects 5-10 days after last administration of IMP.

Statistical methods

No formal sample size calculation has been performed for this trial. The size of the dose group is considered sufficient to provide adequate information on the safety and PK parameters for the purpose of this trial.

All statistical calculations will be performed using the SAS® version 9.4 or later (SAS Institute Inc., Cary, NC, USA). The statistical analyses will only include descriptive statistics reflecting the explorative nature of the trial. In general, the data will be presented by dose group.

Continuous data will be summarised by dose group using number of observations, mean, standard deviation (SD), median, minimum and maximum. Categorical data will be summarised by dose group using the number and percentage of subjects in each category.

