5.2 Sample size calculation

No formal sample size calculation has been performed for this trial. The size of the dose groups is considered sufficient to provide adequate information on the safety and PK parameters for the purpose of this trial.

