5.6 Significance level

All statistical hypotheses in this trial will be answered using two-sided 90% confidence intervals.

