6 CHANGES FROM THE CLINICAL TRIAL PROTOCOL

Changes to the planned analyses and the timing of these are summarised in Table 3.

Table 3 Changes in the planned statistical analyses

| Change category | Timing of change | Description of change | Reason for change |
|--|------------------|--|--|
| Change in the SAP compared to the protocol | Prior to DBL | Added frequency tables for safety laboratory interpretations | To provide a better overview of the safety laboratory data. |
| Change in the SAP compared to the protocol | Prior to DBL | Removed dose proportionality for metabolite M1 | Not relevant with dose proportionality for M1 due to [REDACTED] polymorphism |

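### The SAP turns a dose-proportionality endpoint that the protocol synopsis treats descriptively into a 0.80–1.25 declaration, which two groups of six would usually miss under exact proportionality if the between-subject CV exceeds about 16%

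*SAP*

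**What the plan says.** The protocol synopsis lists, among the primary endpoints, "Dose proportionality after single doses based on" AUC0-t, AUC0-inf and Cmax. It gives no decision rule there. Under Statistical methods it says: "The statistical analyses will only include descriptive statistics reflecting the explorative nature of the trial". It reports no sample size calculation.

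The SAP goes further in four places.

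- Section 5.1 (Statistical hypotheses) presents proportionality of AUC and Cmax to dose as a question to be investigated.
- Section 5.6 adds: "All statistical hypotheses in this trial will be answered using two-sided 90% confidence intervals".
- Section 9.1.1.1 fits a power model, regressing the log PK parameter on log dose, and takes acceptance limits of 0.80 and 1.25 on the dose-normalised ratio, described as "0.8 and 1.25 being the industry standard limits". The rule reads: "Specifically, dose-proportionality is declared when the 90% CI for β_1 from the linear regression model on log scale lies entirely within the acceptance region".
- The Figure PP 1 instruction, carried over to Figures PP 2 and PP 3, asks for a footnote with the regression equation, the slope CI, the acceptance region and one of two conclusions: proportional or not proportional.

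SAP Table 1 applies this analysis to IRL757, M5 and M7. Section 5.2 repeats that no sample size was calculated and adds: "The size of the dose groups is considered sufficient to provide adequate information on the safety and PK parameters for the purpose of this trial". Section 6 states: "Changes to the planned analyses and the timing of these are summarised in Table 3". That table has two entries, the added laboratory frequency tables and the removal of M1 from the dose-proportionality analysis. The declaration rule is not among them.

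**The concern.** The two documents treat one primary endpoint differently. The synopsis calls for description in an exploratory, unsized trial. The SAP adds an equivalence-type decision with two permitted outcomes and does not record it as a change.

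A group size judged adequate for description need not be adequate for an equivalence rule. In parallel groups the error term is between-subject variability, and six subjects per dose give a wide interval. If the interval is wider than the acceptance region, the criterion fails for lack of precision, and the footnote wording turns that failure into a finding that IRL757 or a metabolite is not dose-proportional. A reader could take that as a property of the drug when it is a property of the sample size.

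**Working it through.** **Inputs.** Six subjects per group in a parallel design (SAP 4.1, 4.3), so 10 residual degrees of freedom. Two-sided 90% CI (SAP 5.6). Limits 0.80 and 1.25 (SAP 9.1.1.1). The doses are redacted. The documents give no between-subject CV for AUC or Cmax, so a range of 10% to 40% is assumed. They state no power, so there is no planned figure to reproduce.

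**The dose ratio cancels.** With two dose levels, the slope estimate is (mean ln PK at high dose − mean ln PK at low dose) / ln r. Multiplying (β1 − 1) by ln r gives the log of the dose-normalised geometric mean ratio, r^(β1−1). The SAP rule is therefore the same as requiring the 90% CI of that ratio to lie within 0.80–1.25, for any r. Simulating the SAP regression at r = 1.5, 2, 3 and 5 confirmed this: at CV 20% the declaration rate was 20% at every r.

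**Half-width.** On the log scale, with s the observed pooled SD:

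t(0.95, 10) × s × √(1/6 + 1/6) = 1.8125 × 0.5774 × s = 1.046s

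**Ceiling on the observed SD.** The limit is ln(1.25) = 0.223. Setting 1.046s = 0.223 gives s = 0.213, and √(exp(0.213²) − 1) = 21.6%. If the observed CV is above 21.6%, the interval is wider than the acceptance region and the rule cannot be met, whatever the slope.

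**Chance of declaring.** Let σ = √ln(1 + CV²), k = √(2/6), t = 1.8125 and L = ln(1.25). Under exact proportionality the chance is the integral, over the chi-square-based distribution of s from 0 to L/(tk), of Φ((L − tks)/(σk)) − Φ(−(L − tks)/(σk)). The last column shifts the true ratio to the margin of 1.25. Each figure is for one analyte and one parameter. The CI factor is exp(1.046σ), the amount by which the estimate is divided and multiplied when s equals σ.

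| True CV (assumed) | σ | CI factor | True ratio 1.00 | True ratio 1.25 |
|---|---|---|---|---|
| 10% | 0.100 | 1.11 | 94.9% | 5.0% |
| 15% | 0.149 | 1.17 | 55.9% | 4.9% |
| 20% | 0.198 | 1.23 | 20.3% | 3.8% |
| 25% | 0.246 | 1.29 | 6.0% | 1.9% |
| 30% | 0.294 | 1.36 | 1.7% | 0.7% |
| 40% | 0.385 | 1.50 | 0.2% | 0.1% |

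**Thresholds.** The chance under exact proportionality is 80% at a true CV of 12.3% and 50% at 15.7%. At a true CV of 22% it is about 13%.

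**Scale of the shortfall.** For an 80% chance, the subjects needed per group are 9 at CV 15%, 15 at 20%, 22 at 25% and 31 at 30%. The trial has 6. SAP 4.4 does not replace medical or safety withdrawals. With five subjects in one group and six in the other, the chance is 48.4% at CV 15% and 16.1% at CV 20%.

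**Number of declarations.** Three analytes and three parameters give up to 3 × 3 = 9. The chance that all are declared cannot exceed the lowest single figure.

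**The case against.** The strongest reply is that the full protocol is not available. The SAP refers readers to it, and Table 3 logs the removal of M1 from this very analysis, so someone did compare the dose-proportionality plan with the protocol. The full text may already describe the power model or the criterion. This stands. A reader might infer that the protocol forbids the rule, but the documents show only that the SAP conflicts with an explicit sentence in the synopsis.

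Second, the synopsis does not promise a slope or a confidence interval either. For continuous data it names n, mean, SD, median, minimum and maximum. Read strictly, an estimate with a 90% CI also goes beyond it. This stands too, and it is why the fix below asks for a record in Table 3.

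Third, the CV is unknown. At 10% the rule works well, with a 95% chance of declaring under exact proportionality and 5% at the margin. A reader might infer that the outcome hardly depends on whether exposure is proportional. The table does not support that at low CVs; it is a fair description only from about 25% upwards. A CV below 16% would be low for subjects aged 65 to under 90 and weighing 50 to 110 kg, but that is a judgement and not a figure in the documents.

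Fourth, the uncertainty is not hidden. The slope CI, the acceptance region and the conclusion sit in the same footnote, and geometric means, geometric CVs and CL/F are tabulated by dose. That is correct. The problem is the forced two-way conclusion, not concealment. The documents attach no further decision to it.

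**Conclusion.** The concern holds in conditional form and the SAP should be changed. The SAP sets a formal declaration for an endpoint that the synopsis places under descriptive statistics only, and Table 3 is silent on it. That part does not depend on any CV, but it is shown against the synopsis alone.

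The failure of the rule does depend on CV. Assuming log-normal data, equal variance and all 12 subjects evaluable, the rule would usually be missed under exact proportionality once the true between-subject CV exceeds about 16%. As the SAP is worded, an imprecise interval would then be reported as non-proportionality.

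A reader might take the 21.6% figure as the CV at which the design becomes adequate. It is not: it is the ceiling on the observed CV, above which declaration is impossible. An 80% chance needs a true CV of about 12% or less.

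**What to change.** In SAP 5.1, 5.6, 9.1.1.1 and the Figure PP 1–3 footnotes, remove the declaration and the two-way conclusion. For IRL757, M5 and M7, report β1 and the dose-normalised geometric mean ratio r^(β1−1), each with a 90% CI, as descriptive estimates, preferably in a table. Keep 0.80 and 1.25 as reference lines only. If the full protocol does not already describe this model-based analysis, record it in Table 3.

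If the sponsor prefers to keep the rule:

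- enter it in Table 3;
- report any CI not wholly inside the limits as proportionality not demonstrated, rather than as non-proportionality;
- state in 5.2 that an 80% chance of declaring under exact proportionality needs a true between-subject CV of about 12% or less, and a 50% chance about 16%.

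Either route changes wording only. The model, data, subjects and procedures stay the same. The price of the preferred route is the formal claim of dose proportionality.

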9.2 Analysis of secondary endpoints

9.2.1 Adverse Events (AEs)

AEs and serious AEs (SAEs) will be recorded from the time when informed consent is obtained until the Follow-up Visit. AEs that occur before first treatment with IMP (baseline symptoms) will be listed separately.

All AEs will be described in terms of the dose at which they occurred. AEs will be summarised by System Organ Class (SOC) and Preferred Term (PT) using the Medical Dictionary for Regulatory Activities (MedDRA) vocabulary. The number of subjects reporting AEs, and the number of AEs reported will be presented. The events will be tabulated by SOC, PT and by severity and relationship to IMP. SAEs will be presented in the same tabulations.

9.2.2 *Physical examinations*

Normal and abnormal findings will be specified and summarised by dose group.

9.2.3 *Electrocardiogram (ECG)*

All continuous ECG data will be listed for each subject and summarised by dose group. In addition, ECGs will be categorised as "normal", "abnormal, not clinically significant", or "abnormal, clinically significant" (as judged by the Investigator) and summarised by dose group.

9.2.4 *Vital signs*

Vital signs (blood pressure, heart rate, respiratory rate and body temperature) will be summarised by dose group.

9.2.5 *Safety laboratory analyses*

Safety laboratory data will be summarised by dose group. Safety laboratory interpretations will be summarised by dose groups using frequency tables.

9.2.6 *Columbia-Suicide Severity Rating Scale (C-SSRS)*

This rating scale will be administered for screening of suicidal ideation and behaviour throughout the trial. No formal statistical analysis of the outcome will be performed, i.e., the data will be listed only. Any abnormal findings will be listed and treated as AEs or SAEs.

9.3 *Analysis of exploratory endpoints*

The analysis and results pertaining to the exploratory endpoints, plasma and urine metabolite profiles, will be detailed in a separate report, and hence are not covered in this SAP.

9.4 *Description of trial population*

9.4.1 *Disposition*

A subject disposition will be presented showing the number of screened subjects; the number of withdrawn subjects prior to dose, including the reason for withdrawal; the number of included subjects in each dose group; the number of withdrawn subjects, including the reason for withdrawal; the number of completed subjects; the number of subjects included in the analysis sets, and the number of subjects at each visit.

9.4.2 *Demographics and baseline characteristics*

Descriptive statistics of demographics and other baseline characteristics will be presented by dose group.

9.4.3 *Medical history and concomitant medication*

Medical/surgical history and prior/concomitant medications will be presented by dose group.

Medications are classified as prior if the stop date and time was before or on the day of the dose administration (pre-dose) and as concomitant if ongoing on the day of the dose administration, stopped after the dose administration or started after the dose administration. To distinguish between prior and concomitant medications on the dosing day, the start time of any newly introduced medication or the stop time of any previously ongoing medication will be considered.

Medical/surgical history will be summarised by SOC and PT using the MedDRA vocabulary.

Prior and concomitant medications will be summarised by anatomical therapeutic chemical (ATC) classification and active ingredients using the World Health Organisation (WHO) WHODrug Global drug reference dictionary.

9.4.4 *Treatment compliance*

The subjects treated in each dose group and their individual doses will be listed.

9.5 *Interim analysis*

No formal interim analysis will be performed.

10 DATA DISPLAY PLAN

Tables and figures will only be generated if sufficient data, with sufficient variability exist to justify specific output being produced. Unscheduled/extra visits will generally not be presented in tables and summary figures but will be included in listings.

10.2 Trial tables

10.2.1 Demographic data

Table DM 1 Baseline characteristics and demographics (Full analysis set)

| Assessment (unit) | | IRL757 [REDACTED] (N=6) | IRL757 [REDACTED] (N=6) | Total (N=12) |
|--------------------------------------|----------------------------------|-------------------------------|-------------------------------|--------------------|
| Age (years) | n | x | x | x |
| | Mean (SD) | xx.x (xx.x) | xx.x (xx.x) | xx.x (xx.x) |
| | Median (Min, Max) | xx.x (xx, xx) | xx.x (xx, xx) | xx.x (xx, xx) |
| Height (cm) | n | x | x | x |
| | Mean (SD) | xxx.x (xx.x) | xxx.x (xx.x) | xxx.x (xx.x) |
| | Median (Min, Max) | xxx.x (xxx, xxx) | xxx.x (xxx, xxx) | xxx.x (xxx, xxx) |
| Weight (kg) | n | x | x | x |
| | Mean (SD) | xx.xx (xx.xx) | xx.xx (xx.xx) | xx.xx (xx.xx) |
| | Median (Min, Max) | xx.xx (xx.x, xx.x) | xx.xx (xx.x, xx.x) | xx.xx (xx.x, xx.x) |
| Body Mass Index (kg/m ²) | n | x | x | x |
| | Mean (SD) | xx.xx (xx.xx) | xx.xx (xx.xx) | xx.xx (xx.xx) |
| | Median (Min, Max) | xx.xx (xx.x, xx.x) | xx.xx (xx.x, xx.x) | xx.xx (xx.x, xx.x) |
| Sex | Female | xx (xx%) | xx (xx%) | xx (xx%) |
| | Male | xx (xx%) | xx (xx%) | xx (xx%) |
| Ethnicity | Hispanic or latino | xx (xx%) | xx (xx%) | xx (xx%) |
| | Not hispanic or latino | xx (xx%) | xx (xx%) | xx (xx%) |
| | Not reported | xx (xx%) | xx (xx%) | xx (xx%) |
| | Unknown | xx (xx%) | xx (xx%) | xx (xx%) |
| Race | American Indian or Alaska Native | xx (xx%) | xx (xx%) | xx (xx%) |
| | Asian | xx (xx%) | xx (xx%) | xx (xx%) |
| | Black or African American | xx (xx%) | xx (xx%) | xx (xx%) |

| Assessment (unit) | IRL757 (N=6) | IRL757 (N=6) | Total (N=12) |
|---|-----------------|-----------------|-----------------|
| Native Hawaiian or Other Pacific Islander | xx (xx%) | xx (xx%) | xx (xx%) |
| White | xx (xx%) | xx (xx%) | xx (xx%) |

Data based on [ANALYSIS SET]. N: number of subjects in treatment group. Mean values and percentages are based on n. n: Number of observations.

SD: Standard deviation. SAS program: [PROGRAM NAME].sas.

Dataset version: ADXX YYYY-MM-DDTHH:MM:SS. Run by: [USERNAME] YYYY-MM-DDTHH:MM:SS. EDC data extracted: YYYY-MM-DDTHH:MM:SS.

Table DS 1 Subject disposition (All subjects)

| | Total (N=12) |
|--|-----------------|
| Screened subjects | xxx |
| Withdrawn prior to dose | xxx |
| Reason for withdrawal prior to dose | |
| --- Reason 1 | xxx |
| --- Reason 2 | xxx |
| --- ... | xxx |
| Subjects included in trial | xxx |
| Allocated to arm | |
| --- IRL757 [REDACTED] | xxx |
| --- IRL757 [REDACTED] | xxx |
| Withdrawn subjects | |
| --- Reason 1 | xxx |
| --- Reason 2 | xxx |
| --- ... | xxx |
| Completed subjects | xxx |
| Included in Full analysis set | xxx |
| Included in Pharmacokinetic analysis set | xxx |
| Subjects at each visit | |
| --- Visit 1 - Screening | xxx |
| --- Visit 2 - In-clinic | xxx |
| --- Follow-up visit - Ambulatory | xxx |

Data based on All subjects. SAS program: [PROGRAM NAME].sas.

Dataset version: ADXX YYYY-MM-DDTHH:MM:SS. Run by: [USERNAME] YYYY-MM-DDTHH:MM:SS. EDC data extracted: YYYY-MM-DDTHH:MM:SS.

Table MH 1 Medical history events by system organ class and preferred term (Full analysis set)

| System organ class Preferred term | IRL757 (N=6) | IRL757 (N=6) | Total (N=12) | | | |
|--------------------------------------|-----------------|-----------------|-----------------|-----------|-----------------|-----------|
| | n (%) | m | n (%) | m | n (%) | m |
| Total | xx (xx%) | xx | xx (xx%) | xx | xx (xx%) | xx |
| [SOC 1] | xx (xx%) | xx | xx (xx%) | xx | xx (xx%) | xx |
| [SOC 1 PT 1] | xx (xx%) | xx | xx (xx%) | xx | xx (xx%) | xx |
| [SOC 1 PT 2] | xx (xx%) | xx | xx (xx%) | xx | xx (xx%) | xx |
| [SOC 1 PT ...] | xx (xx%) | xx | xx (xx%) | xx | xx (xx%) | xx |
| [SOC 2] | xx (xx%) | xx | xx (xx%) | xx | xx (xx%) | xx |
| [SOC 2 PT 1] | xx (xx%) | xx | xx (xx%) | xx | xx (xx%) | xx |
| [SOC 2 PT 2] | xx (xx%) | xx | xx (xx%) | xx | xx (xx%) | xx |
| [SOC 2 PT ...] | xx (xx%) | xx | xx (xx%) | xx | xx (xx%) | xx |
| [SOC ...] | xx (xx%) | xx | xx (xx%) | xx | xx (xx%) | xx |
| [SOC ... PT 1] | xx (xx%) | xx | xx (xx%) | xx | xx (xx%) | xx |
| [SOC ... PT 2] | xx (xx%) | xx | xx (xx%) | xx | xx (xx%) | xx |
| [SOC ... PT ...] | xx (xx%) | xx | xx (xx%) | xx | xx (xx%) | xx |

Data based on [ANALYSIS SET]. N: number of subjects in treatment group. Percentages are based on N. n: number of subjects. m: number of events. The following events are coded with multiple terms and are represented as separate events in tables and listings: '[MH TERM 1], [MH TERM 2]'. See listings for detailed information. SAS program: [PROGRAM NAME].sas.
Dataset version: ADXX YYYY-MM-DDTHH:MM:SS. Run by: [USERNAME] YYYY-MM-DDTHH:MM:SS. EDC data extracted: YYYY-MM-DDTHH:MM:SS.

Table CM 1 Prior medications by ATC classification and active ingredients (Full analysis set)

| ATC classification | IRL757 [REDACTED] (N=6) | IRL757 [REDACTED] (N=6) | Total (N=12) | | | |
|---|-------------------------------|-------------------------------|-----------------|-----------|-----------------|-----------|
| Active Ingredients | n (%) | m | n (%) | m | n (%) | m |
| Total | xx (xx%) | xx | xx (xx%) | xx | xx (xx%) | xx |
| [ATC classification 1] | xx (xx%) | xx | xx (xx%) | xx | xx (xx%) | xx |
| [ATC classification 1 Active Ingredients 1] | xx (xx%) | xx | xx (xx%) | xx | xx (xx%) | xx |
| [ATC classification 1 Active Ingredients 2] | xx (xx%) | xx | xx (xx%) | xx | xx (xx%) | xx |
| [ATC classification 1 Active Ingredients ...] | xx (xx%) | xx | xx (xx%) | xx | xx (xx%) | xx |
| [ATC classification 2] | xx (xx%) | xx | xx (xx%) | xx | xx (xx%) | xx |
| [ATC classification 2 Active Ingredients 1] | xx (xx%) | xx | xx (xx%) | xx | xx (xx%) | xx |
| [ATC classification 2 Active Ingredients 2] | xx (xx%) | xx | xx (xx%) | xx | xx (xx%) | xx |
| [ATC classification 2 Active Ingredients ...] | xx (xx%) | xx | xx (xx%) | xx | xx (xx%) | xx |
| [ATC classification ...] | xx (xx%) | xx | xx (xx%) | xx | xx (xx%) | xx |
| [ATC classification ... Active Ingredients 1] | xx (xx%) | xx | xx (xx%) | xx | xx (xx%) | xx |
| [ATC classification ... Active Ingredients 2] | xx (xx%) | xx | xx (xx%) | xx | xx (xx%) | xx |
| [ATC classification ... Active Ingredients ...] | xx (xx%) | xx | xx (xx%) | xx | xx (xx%) | xx |

Data based on [ANALYSIS SET]. N: number of subjects in treatment group. Percentages are based on N. n: number of subjects. m: number of events. The following records are coded with multiple terms and are represented as separate events in tables and listings: '[CM TERM 1], [CM TERM 2]'. See listings for detailed information. SAS program: [PROGRAM NAME].sas. Dataset version: ADXX YYYY-MM-DDTHH:MM:SS. Run by: [USERNAME] YYYY-MM-DDTHH:MM:SS. EDC data extracted: YYYY-MM-DDTHH:MM:SS.

Table CM 2 Concomitant medications by ATC classification and active ingredients (Full analysis set)

Same layout as Table CM 1

